#### 10.2.3.2. Secondary Efficacy Analyses

The secondary efficacy analyses will be performed based on the FAS.

The first secondary efficacy endpoint will only be addressed with statistical hypothesis tests if the primary endpoint is statistically significant using the full overall 2.5% one-sided alpha. If the first secondary endpoint is also statistically significant, the full 2.5% one-sided alpha will be passed to the 4 remaining secondary endpoints. Multiplicity in the secondary endpoints will be addressed with the fallback method. 60-day mortality will be analyzed similar to 28-day mortality and the other secondary endpoints will be evaluated using a logistic regression model with the explanatory variables randomized treatment arm (Arm B versus Arm A) and age for:

1. 60-day all-cause mortality
2. Proportion of patients with an improvement in the provided 8-point ordinal scale at day 15 (at least one score point lower than at randomization)
3. Proportion of patients with an improvement in the provided 8-point ordinal scale at day 28 (at least one score point lower than at randomization)
4. Proportion of patients developing acute kidney failure ( $eGFR < 15 \text{ mL/min}/1.73\text{m}^2$ ) during ICU stay and at day 28
5. Proportion of patients free of any renal replacement therapy within 28 days upon randomization
- 6.

The ordering of the secondary endpoints 2 to 5 for hypothesis testing will be as in above mentioned list. The full 2.5% one-sided alpha for the fallback method will be attributed to the 4 secondary endpoints in the following way 2%, 0.2%, 0.2%, and 0.1%. If the preceding hypothesis test is not significant, subsequent tests will be performed at the aforementioned alpha level. If tests are significant, the alpha is added to the subsequent hypothesis test (e.g., if the primary hypothesis test is significant and secondary endpoints 1-4 are all significant, the fifth secondary endpoint will be tested at an alpha of 2.5%; if the fourth secondary endpoint is not significant, the fifth secondary endpoint will be tested at an alpha of 0.1%).

The primary endpoint as well as all secondary endpoints will also be evaluated as censored time to event variables by Kaplan-Meier type methods. Kaplan-Meier analyses will be performed comparing the two treatment arms overall and within the following stratifications:

- Stratification by site
- Stratification by country

- Stratification by sex
- Stratification by age
- Stratification by comorbidities
- Stratification by standard or care.

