The z-statistic for the interim and final analysis will be calculated as the proportion of the beta coefficient for the treatment arm effect and its standard error from the Cox proportional hazards regression model. The study will be stopped for futility if the z-statistic for the first stage is 0 or lower.

The first secondary efficacy endpoint will only be addressed with statistical hypothesis tests if the primary endpoint is statistically significant, using the full overall 2.5% one-sided alpha. If the first secondary endpoint is also statistically significant, the full 2.5% one-sided alpha will be passed to the 4 remaining secondary endpoints. Multiplicity in the secondary endpoints will be addressed with the fallback method. 60-day mortality will be analyzed similar to 28-day mortality, and the other secondary endpoints will be evaluated using a logistic regression model with the explanatory variables randomized treatment arm (Arm B versus Arm A) and age:

1. 60-day all-cause mortality
2. Proportion of patients with an improvement in the provided 8-point ordinal scale at day 15 (at least one score point lower than at randomization)
3. Proportion of patients with an improvement in the provided 8-point ordinal scale at day 28 (at least one score point lower than at randomization)
4. Proportion of patients developing acute kidney failure ( $eGFR < 15 \text{ mL/min/1.73m}^2$ ) during ICU stay and at day 28
5. Proportion of patients free of any renal replacement therapy within 28 days upon randomization

The ordering of the secondary endpoints 2 to 5 for hypothesis testing will be as in above mentioned list. The full 2.5% one-sided alpha for the fallback method will be attributed to

these 4 secondary endpoints in the following way: 2%, 0.2%, 0.2%, and 0.1%. If the preceding hypothesis test is not significant, subsequent tests will be performed at the aforementioned alpha level. If tests are significant, the alpha is added to the subsequent hypothesis test (e.g., if the primary hypothesis test is significant and secondary endpoints 1-4 are all significant, the fifth secondary endpoint will be tested at an alpha of 2.5%; if the fourth secondary endpoint is not significant, the fifth secondary endpoint will be tested at an alpha of 0.1%).

The primary endpoint as well as all secondary endpoints will also be evaluated as censored time to event variables by Kaplan-Meier type methods.

Safety:

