##### **4.2.2.2. Secondary Endpoints**

The secondary endpoints in Phase III are:

- 60-day all-cause mortality (proportion of patients deceased until Day 60)
- Proportion of patients with an improvement in the 8-point ordinal scale (Appendix 7) (day 15, day 28)
- Proportion of patients developing acute kidney failure (eGFR < 15 mL/min/1.73m^2, assessed by the CKD-EPI equation requiring race information) during ICU stay and at day 28
- Proportion of patients free of any renal replacement therapy within 28 days upon randomization
- Frequency, severity, and relatedness to study drug of serious and non-serious TEAEs

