### 6.2.2. Exclusion Criteria

Patients who fulfill any of the following criteria at randomization are not eligible to participate in Phase III of the study:

1. Intubated > 48 h at time point of first IMP administration
2. Expected stop of invasive ventilation or expected extubation in the next 24h without additional intervention according to judgment of the investigator
3. Known history of chronic dialysis OR received renal replacement therapy in past 14 days OR anticipated to receive renal replacement therapy within 24h after randomization
4. Known history of progressed COPD as evidenced by use of daily maintenance treatment with long-acting bronchodilators or inhaled/oral corticosteroids for > 2 months
5. Treatment of COVID-19 with investigational antibody treatment(s) which are not approved or not included in locally adopted treatment guidelines (e.g., WHO guidance, National Institutes of Health [NIH] COVID-19 treatment guidelines) for this indication in the past 7 days (Note: Antibody treatment[s] given within past 7 days for pre-existing diseases, other than COVID-19, are allowed.)
6. At time point of randomization, treatment of COVID-19 with investigational treatments which are not approved or not included in locally adopted treatment guidelines for this indication (e.g., WHO guidance, NIH COVID-19 treatment guidelines), including SARS-CoV-2 multiplication inhibitor(s) or immunomodulator(s). (Note: If a locally adopted treatment guideline recommends drugs such as remdesivir, dexamethasone, or anticoagulation, this would be allowed. Adopted guidelines and updates must be documented at study initiation and throughout the conduct of the study.)
7. Received cytokine adsorption therapy in past 3 days

8. Known hypersensitivity to IFX-1 or any other ingredient of the study medication
9. Serum or urine pregnancy test positive before randomization (required for women of childbearing potential)
10. Received organ or bone marrow transplantation in past 3 months
11. Known cardio-pulmonary mechanical resuscitation in past 14 days
12. Patient moribund or expected to die in next 24h according to the judgment of the investigator
13. Known to have received anti-cancer therapy for hemato-oncological disease in past 4 weeks  
OR known to have active malignant disease at time point of randomization
14. Known severe congestive heart failure (corresponding to e.g. NYHA Class III-IV, left ventricular ejection fraction <40%; see Appendix 8)

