#### **8.2.1. Baseline Assessments (Screening)**

The following procedures will be performed to assess baseline characteristics during screening evaluations and before randomization and IMP administration:

- Check inclusion and exclusion criteria

- Documentation of demographic details (age, gender, race, and ethnicity), medical and COVID-19 history (see Sections 8.2.1.1 and 8.2.1.2). Race information is required for eGFR calculation using the CKD-EPI equation
- 8-point ordinal scale assessment (see Section 8.2.2.2) and oxygenation index ( $\text{PaO}_2 / \text{FiO}_2$ ; one representative measurement within 6h before randomization)
- Documentation of concomitant disease and prior medications (see Sections 8.2.1.3 and 8.2.1.4)
- Baseline safety assessment (height, weight, physical exam, AEs, ECG, urine analysis, pregnancy test, and clinical safety laboratory [including creatinine assessment]); see Section 8.2.3)

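### Secondary endpoints 4 (eGFR < 15) and 5 (free of renal replacement therapy) are adjusted for age only although screening creatinine is collected: the tests are valid but may give up some power

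*Combined protocol and SAP*

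**What the plan says.** All references are to protocol Version 4.0 unless stated.

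- **Model.** Section 10.2.3.2 has endpoints 2 to 5 "evaluated using a logistic regression model with the explanatory variables randomized treatment arm (Arm B versus Arm A) and age for" the listed outcomes. The synopsis gives the same "logistic regression model with the explanatory variables randomized treatment arm (Arm B versus Arm A) and age". Version 2.0 used age, sex and PaO2/FiO2, also without a renal term.
- **Endpoints.** Endpoint 4 is "Proportion of patients developing acute kidney failure" (eGFR < 15 mL/min/1.73m² by CKD-EPI), timed to the ICU stay and day 28. Endpoint 5 is "Proportion of patients free of any renal replacement therapy within 28 days upon randomization".
- **Baseline data.** Section 8.2.1 lists "clinical safety laboratory [including creatinine assessment" among the screening procedures before randomization. It also requires race so that CKD-EPI eGFR can be calculated.
- **Entry.** Exclusion 3 in section 6.2.2 covers known chronic dialysis and patients who "received renal replacement therapy in past 14 days OR anticipated to receive renal replacement therapy within 24h after randomization". There is no eGFR limit.
- **Multiplicity.** 28-day mortality must be significant, then 60-day mortality: "If the first secondary endpoint is also statistically significant, the full 2.5% one-sided alpha will be passed to the 4 remaining secondary endpoints". The one-sided alpha is "attributed to the 4 secondary endpoints in the following way 2%, 0.2%, 0.2%, and 0.1" per cent for endpoints 2, 3, 4 and 5 in that order.
- **Detail left open.** Section 10.2.3 calls itself a summary and leaves exact definitions to a SAP to be finalized before unblinding. The supplied file contains no separate Phase III SAP.

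**The concern.** Endpoint 4 is a threshold on eGFR, and its baseline value is available for use. RRT during follow-up plausibly depends on the same baseline. Without an eGFR limit at entry, baseline renal function may vary widely. Section 5.1.1 names no stratification factor for Phase III, so as written neither the design nor the model accounts for a chance renal imbalance.

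The plan uses the baseline of the outcome elsewhere. The Phase II primary model adjusted oxygenation index for its own baseline (section 10.1.3.1), and ordinal-scale improvement is defined relative to the score at randomization. Less renal impairment was also one of the signals cited from Phase II (section 3.2.3).

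If baseline eGFR is prognostic given age, a logistic model without it has a smaller expected z-statistic for treatment. The cost would fall on two alpha-controlled endpoints that stand last in the sequence.

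**Working it through.** **1. The plan's own figure.** The only stated power is 90% for 28-day mortality: 30% v 15%, 180 per arm, one-sided 2.5%. With continuity correction:

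- d = 0.15 − 1/180 = 0.1444
- SE under the null = √(2 × 0.225 × 0.775/180) = 0.0440
- SE under the alternative = √((0.30 × 0.70 + 0.15 × 0.85)/180) = 0.0433
- power = Φ((0.1444 − 1.96 × 0.0440)/0.0433) = 91.0%

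Fisher's exact test gives 91.5%, and the uncorrected pooled test 92.9%. The stated figure is reproduced closely. It does not involve the renal models, and no power is stated for those.

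**2. Alpha available.** Endpoint 4 starts at 0.2% and can reach 2 + 0.2 + 0.2 = 2.4%. Endpoint 5 starts at 0.1% and can reach 2.4 + 0.1 = 2.5%. Power was therefore taken at 2.5%, 0.2% and 0.1%.

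**3. Simulation.** From the documents: 360 patients, 1:1, logistic model with arm and age. Assumed, because the documents give nothing:

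- renal event rates, control v IFX-1, of 20% v 10%, 30% v 18% and 40% v 27%
- age odds ratio 1.3 per SD
- correlation of 0.4 between age and worse baseline eGFR
- odds ratio (OR) per SD of worse baseline eGFR, given age, from 1 to 4

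The outcome model is logit P(event) = a + b·arm + ln(1.3)·age + ln(OR)·x, with x = 0.4·age + √(1 − 0.4²)·e, where age and e are independent standard normals. The constants a and b were solved to give the stated marginal rates. Each setting had 4,000 trials, analysed by Wald test with and without x.

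Power (%), age only → age plus baseline eGFR, in the order of the three rate pairs:

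| OR per SD | one-sided 2.5% | 0.2% | 0.1% |
|---|---|---|---|
| 1.0 | 75.8→76.1, 76.2→76.5, 74.0→73.9 | 38.6→38.4, 40.2→40.3, 39.9→40.0 | 30.4→30.5, 32.0→32.0, 31.5→31.2 |
| 1.5 | 76.9→77.1, 77.0→78.3, 76.4→77.7 | 40.2→41.6, 41.9→42.9, 40.9→42.4 | 31.1→32.2, 33.9→34.8, 32.7→34.3 |
| 2.0 | 77.9→80.0, 77.8→80.1, 76.6→80.1 | 41.0→43.9, 44.3→47.9, 40.9→44.4 | 31.8→35.0, 35.3→38.7, 32.8→36.8 |
| 3.0 | 77.6→83.1, 79.1→84.5, 78.9→85.1 | 41.9→48.4, 43.3→51.4, 44.1→53.6 | 33.2→38.9, 34.4→42.5, 35.7→45.4 |
| 4.0 | 79.4→85.8, 79.1→87.2, 77.9→87.0 | 42.0→53.4, 44.0→56.7, 42.4→56.4 | 32.6→43.8, 35.2→47.5, 34.8→47.6 |

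Gains by subtraction, in percentage points:

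| OR per SD | 2.5% | 0.2% | 0.1% |
|---|---|---|---|
| 1.0 | −0.1 to 0.3 | −0.2 to 0.1 | −0.3 to 0.1 |
| 1.5 | 0.2 to 1.3 | 1.0 to 1.5 | 0.9 to 1.6 |
| 2.0 | 2.1 to 3.5 | 2.9 to 3.6 | 3.2 to 4.0 |
| 3.0 | 5.4 to 6.2 | 6.5 to 9.5 | 5.7 to 9.7 |
| 4.0 | 6.4 to 9.1 | 11.4 to 14.0 | 11.2 to 12.8 |

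The squared ratio of mean z-statistics gives the equivalent gain in sample size: about 2 to 3% for OR 1.5, 5 to 8% for 2, 13 to 18% for 3 and 20 to 25% for 4.

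**4. Second simulation.** With assumed rates of 25% v 14% and odds ratios of 2.0, 2.7 and 4.1, power rose from 75–76% to 79%, 81% and 85% at 2.5%. At 0.2% it rose from 39–40% to 43%, 47% and 53%. The pattern is the same.

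**The case against.** The strongest reply is that nothing here is an error. Under randomization the age-only test keeps its type I error. Its odds ratio differs from one conditional on eGFR because odds ratios are not collapsible, so the smaller value is not a biased estimate. Arm plus age is also the common covariate set for mortality, the ordinal scale, extubation and the Glasgow Outcome Scale. All of that stands.

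The consequence is also limited. The renal tests lie behind two mortality tests, and the alpha split costs more than the missing covariate. At an odds ratio of 2 with age only, moving from 2.5% to 0.2% lowers power by about 33 to 37 points (for example 77.9 − 41.0 = 36.9), against the 3 to 4 points the covariate would recover at 0.2%. Age enters CKD-EPI and the RRT exclusions may narrow the baseline range, so a weak added effect is possible. The simulations also ignore death, and the plan does not say how deaths count in endpoints 4 and 5. These points limit the size, but they give no reason to leave a collected baseline value unused.

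A reader might go further and infer that patients already below eGFR 15 at entry are bound to count as events in both arms and so dilute the comparison. The documents do not support that. Developing can mean new onset, and the definition joins the ICU stay and day 28 with 'and', so a patient who recovers by day 28 may not count. The exact definition is left to the SAP, and the documents do not say how many such patients would be enrolled.

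**Conclusion.** The point holds as one of efficiency. The models for endpoints 4 and 5 omit a baseline renal measure that the trial can supply. The tests are valid, with neither bias nor type I error inflation. The loss ranges from nothing, if eGFR adds nothing to age, to about 9 points at one-sided 2.5% and 14 points at 0.2% if the odds ratio per SD is 4. For odds ratios of 1.5 to 2 it is about 0 to 4 points at any of the three levels.

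The direction is well supported, since endpoint 4 is a threshold on the same measure. The size is not: event rates, prognostic strength and the age correlation are all assumptions. The point has practical effect only if 28-day and 60-day mortality are both significant, and only if the SAP does not already include the covariate.

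**What to change.** Before unblinding:

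- Add screening eGFR (or log creatinine) alongside age in the logistic models for endpoints 4 and 5.
- Name the pre-randomization screening value. Under Table 2 the Day 1 visit may fall up to 24 hours after randomization.
- State a simple rule for missing baseline values, such as imputing the screening mean pooled over both arms, so that no patient leaves the analysis.
- Keep the full analysis set as the population. An analysis of endpoint 4 limited to patients with screening eGFR ≥ 15 can be a sensitivity analysis.
- Align section 10.2.3.2, the synopsis and the SAP, and note that the reported odds ratio is then conditional on age and baseline renal function.

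No new data or patients are needed. The cost is a protocol text change as well as SAP wording, late in the trial: Version 4.0 is dated 12 May 2021 and last follow-up is expected in August 2021.

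### The secondary-endpoint fallback is valid at 2.5% one-sided but discards any alpha still held when endpoint 5 is rejected; one return transfer from endpoint 5 to endpoint 2 would use it at no cost in error control.

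*Combined protocol and SAP*

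**What the plan says.** Section 10.2.3.2 of protocol Version 4.0 sets two gates. For 60-day mortality: "The first secondary efficacy endpoint will only be addressed with statistical hypothesis tests if the primary endpoint is statistically significant". If that is also significant, "the full 2.5% one-sided alpha will be passed to the 4 remaining secondary endpoints".

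Within that family, "Multiplicity in the secondary endpoints will be addressed with the fallback method". The four endpoints are ordinal-scale improvement at day 15 (endpoint 2), ordinal-scale improvement at day 28 (endpoint 3), acute kidney failure (endpoint 4) and freedom from renal replacement therapy to day 28 (endpoint 5). The order is fixed: "The ordering of the secondary endpoints 2 to 5 for hypothesis testing will be as in above mentioned list". The alpha is "attributed to the 4 secondary endpoints in the following way 2%, 0.2%, 0.2%, and 0.1" (percent).

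Two rules govern the levels. After a significant result, "If tests are significant, the alpha is added to the subsequent hypothesis test". After a non-significant one, "If the preceding hypothesis test is not significant, subsequent tests will be performed at the aforementioned alpha level". The synopsis repeats the split and both rules. Neither place says what happens to alpha remaining after endpoint 5, and neither provides for retesting an earlier endpoint.

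**The concern.** Alpha moves 2 to 3 to 4 to 5 and then leaves the family. Suppose endpoint 2 narrowly misses 2% and endpoints 3, 4 and 5 are all rejected. Endpoint 5 then holds 0.5 points, which no longer protect anything, while endpoint 2 stays at 2.0%. The plan gives endpoint 2 80% of the family's alpha (2.0 of 2.5 points), yet it is the one endpoint that can never receive any back. Endpoints 3 and 4 can also be stranded below 2.5% when they are the only endpoint left.

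At stake is a secondary claim that 2.5% family-wise control would allow but the written rule does not. Neither mortality test is affected.

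**Working it through.** **Inputs** (section 10.2.3.2): initial levels 2.0%, 0.2%, 0.2% and 0.1% for endpoints 2 to 5, fixed order, forward transfer only.

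**Reproducing the plan's figures.** 2.0 + 0.2 + 0.2 + 0.1 = 2.5%. If every preceding test is significant, endpoint 5 is tested at 2.5%. If endpoint 4 is not significant, endpoint 5 is tested at its own 0.1%. Both match the plan's worked example.

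**Exact check by closed testing.** Take any set of endpoints not yet rejected. Under the plan, each has its own alpha plus that of the run of rejected endpoints immediately before it. Alpha belonging to endpoints after the last open one has nowhere to go:

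| Last open endpoint | Number of sets | Alpha discarded | Alpha used |
|---|---|---|---|
| 2 | 1 | 0.2 + 0.2 + 0.1 = 0.5 | 2.0% |
| 3 | 2 | 0.2 + 0.1 = 0.3 | 2.2% |
| 4 | 4 | 0.1 | 2.4% |
| 5 | 8 | 0 | 2.5% |

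So 7 of the 15 intersection hypotheses use less than 2.5%.

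Now add one transfer from 5 to 2 with weight 1. Alpha goes to the next open endpoint in cyclic order, so every one of the 15 sets uses exactly 2.5%. No level falls, because the discarded amount is simply added to the first open endpoint. Two results follow, whatever the effects or correlations:

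- Bonferroni on each intersection keeps family-wise error at or below 2.5%.
- Every rejection under the plan is also a rejection under the revised rule.

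**Levels on retest.** With endpoint 2 open:

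- 3, 4 and 5 rejected: 2.5%.
- Only 4 and 5 rejected: 2.3%.
- Only 5, or 3 and 5, rejected: 2.1%.

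With only endpoint 3 open the level moves from 2.2% to 2.5%, and with only endpoint 4 open from 2.4% to 2.5%.

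**Two sets of p-values (endpoints 2 to 5).**

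- 0.022, 0.001, 0.001, 0.0005. As written, endpoint 2 fails at 0.020; endpoints 3, 4 and 5 are rejected at 0.002, 0.004 and 0.005. Revised, endpoint 2 is retested at 0.020 + 0.005 = 0.025, and all four are rejected.
- 0.010, 0.023, 0.001, 0.0005. As written, endpoint 3 fails at 0.022; endpoints 2, 4 and 5 are rejected. Revised, endpoint 3 is retested at 0.022 + 0.003 = 0.025, and all four are rejected.

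**Size.** The documents give no effects or correlations for these endpoints, so the values below are assumptions: mean z-statistics for endpoints 2 to 5, common correlation 0.3 to 0.7, 400,000 simulated vectors per setting, all conditional on passing both mortality tests.

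| Mean z (2, 3, 4, 5) | Trials with an extra rejection | Power for endpoint 2 |
|---|---|---|
| 2.8 for all | 0.5% to 1.0% | 77.2% to 77.5–77.8% |
| 3.2 for all | 0.4% to 1.0% | gain 0.3 to 0.6 points |
| 2.0, 3.5, 3.0, 3.0 | 1.8% to 2.0% | about 48% to 49.5–50.0% |
| 2.2, 3.0, 3.5, 3.5 | 2.4% to 2.5% | about 56% to 58% |
| 2.8, 2.8, 1.5, 1.5 or 3.0, 2.5, 1.5, 1.5 | 0.02% to 0.1% | gain under 0.1 point |
| 2.0, 4.0, 4.0, 4.0 (favourable) | 3.2% to 3.4% | about 48% to 51.0–51.4% |

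No simulated trial lost a rejection. Under the global null the chance of any false rejection was the same for both rules (2.2% to 2.5%), as it must be: the extra transfer acts only after endpoint 5 has been rejected.

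**Ceiling.** Endpoint 2 gains only if 0.020 < p ≤ 0.025. With mean z equal to μ, that probability is Φ(μ − 1.960) − Φ(μ − 2.054), which peaks near μ = 2 at 0.037. Its power can therefore never rise by more than 3.7 points.

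**The case against.** The strongest reply is that nothing here is wrong. The plan names the fallback method, which passes alpha forward by construction. Its weights sum to 2.5%, its examples reproduce, and exhausting alpha is not a requirement. That stands: this is a choice between two valid procedures.

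The useful region is also narrow. Any gain requires rejecting endpoint 5. If endpoint 2 has missed 2%, the full 0.5 points return only if endpoints 3, 4 and 5 reach p ≤ 0.002, 0.004 and 0.005, and endpoint 2 must then lie between 0.020 and 0.025. The larger gains arise where endpoint 2 is assumed to be the weakest of the four; with weak renal effects the gain all but vanishes. That stands too.

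A third reply is cost. According to Appendix 13, Version 4.0 (12 May 2021) reordered the secondary endpoints after regulatory scientific advice, and the synopsis expects last follow-up in August 2021. Reopening the text that late takes effort. This bears on priority rather than substance, since the change keeps the agreed order and initial weights.

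A reader might infer that all alpha released by endpoints 3 to 5 is lost. It is not: alpha from 3 is used at 4, and alpha from 4 at 5, and it is lost only once endpoint 5 is rejected. A reader might also infer that sending alpha from 3 and 4 straight back to 2 would be at least as good. It would not. With p = 0.03, 0.001, 0.003, 0.02, the plan rejects 3 and 4 (endpoint 4 at 0.004). Direct return leaves endpoint 4 at 0.002 and rejects only 3.

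**Conclusion.** The point holds as an optional improvement. The fallback controls one-sided family-wise error at 2.5% but is not alpha-exhaustive: 7 of 15 intersections leave 0.1 to 0.5 points unused. A single return transfer from endpoint 5 to endpoint 2 removes the waste with the same error control and no lost rejection. That part is exact and needs no assumptions.

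The size does rest on assumptions. Among trials that pass both mortality tests, roughly 0.02% to 2.5% gain a rejection, or about 3.4% when endpoint 2 is borderline and the other three are very strong. The gain in power for endpoint 2 is typically 0 to about 2 points, with a ceiling of 3.7. As a share of all trials the figures are smaller, because both mortality tests must succeed first.

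The documents do not support reading this as an inflated error rate, an invalid procedure or a problem with the primary analysis.

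**What to change.** In section 10.2.3.2, the synopsis and the SAP, keep the order, the initial 2%/0.2%/0.2%/0.1% and the forward transfers 2 to 3, 3 to 4 and 4 to 5 with weight 1. Add one transfer from 5 to 2 with weight 1, and state that the standard graphical update algorithm applies, so that an endpoint not yet rejected is retested whenever its level rises. Do not replace the forward transfers from 3 or 4 with direct returns to 2.

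The cost is a sentence or two in each place and a small change to the testing program. Sample size, endpoints, both mortality tests and data collection are unaffected. Because two of the places are protocol text, it needs a protocol amendment; given the small gain, it is best carried with another change. It must be in place before unblinding, which is also when section 10.2.3 requires the SAP to be final, because recycling added after results are known would not be credible.
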